6.2.1.1 DISPENSING OF TGR-1202(UMBRALISIB)

Before dispensing, the site pharmacist or his/her representative must check that the TGR-1202 is in accordance with the product specifications and the validity is within the re-test date.

The exact dose and the date of administration of TGR-1202 must be recorded within the eCRF, patient's medical records, and/or in the drug accountability records. For the purpose of drug accountability and dosing subjects should record any missed doses of TGR-1202 on a drug diary. Any error in drug administration should be recorded (e.g., missed dose) in the eCRF.

The Pharmacist or his/her representative should record the date dispensed and patient's number and initials, as well as complete the accountability record in the electronic drug accountability system with information concerning the dispensation of TGR-1202.

6.2.2 CRITERIA FOR ONGOING TREATMENT

Continue treatment as per protocol provided that patient has:

- No intolerable toxicities related to study drug.
 - Treatment may be delayed to recover from toxicity for a maximum of one cycle.
- No clinical or radiographic evidence of disease progression.
- Not withdrawn from the study for other reasons.

6.3 DOSING DELAYS AND MODIFICATIONS

Patients should be assessed clinically for toxicity at each visit using the NCI CTCAE v4.0 (http://evs.nci.nih.gov/ftp1/CTCAE/CTCAE_4.03_2010-06-14_QuickReference_8.5x11.pdf) grading scale. Dose delay and/or modification guidance is for adverse events considered at least possibly related to the study drug. If cytopenias are deemed related to the underlying disease rather than study drug, dose modifications are not required, or are per investigator discretion.

A maximum one cycle delay of treatment (28 days) for recovery from toxicity is allowed to recover from hematologic toxicities to \leq Grade 3 or non-hematologic toxicities to \leq Grade 2 or to baseline level. If greater than a one cycle delay is necessary, then the patient should discontinue treatment and continue to be followed for progression. If a patient withdraws consent or has documented progression, an end of study visit should be completed.

6.3.1 DOSE DELAY/MODIFICATION RECOMMENDATIONS: TGR-1202

Supportive care should be considered for any patient who experiences Grade \geq 2 cytopenias, or Grade \geq 1 non-hematologic toxicities. A maximum 28 day (1 cycle) delay for recovery from toxicity is allowed to allow recovery of hematologic toxicities to \leq Grade 3 or non-hematologic toxicities to \leq Grade 2 or to baseline level. If greater than a 28- day delay is necessary, then the patient should discontinue treatment and continue to be followed for progression. If the patient withdraws consent or has documented progression, an end of study visit should be completed.

TABLE 1: TGR-1202(UMBRALISIB) DOSE DELAY AND/OR MODIFICATIONS GUIDANCE

NCI-CTCAE Grade	Dose Delay and/or Modification
Hematologic Adverse Event	
Neutropenia	
Grade \leq 2 neutropenia	Maintain current dose. Consider supportive care as warranted.
Grade 3 neutropenia	Maintain current dose, consider supportive care. If recurrence or persistent Grade 3, resume at next lower dose level at discretion of the investigator.
Grade 4 neutropenia or occurrence of neutropenic fever or infection	
Delay TGR-1202 until Grade \leq 3 and/or neutropenic fever or infection is resolved; thereafter, resume at full dose. Consider supportive care. If delay is $>$ 28 days discontinue study drug.
 
If recurrence after rechallenge, resume at next lower dose level at discretion of the investigator.

Thrombocytopenia	
Grade \leq 3 thrombocytopenia	Maintain current dose level and provide supportive care as clinically warranted.
Grade 4 thrombocytopenia	
Delay TGR-1202 until Grade \leq 3; thereafter, resume at full dose. Consider supportive care intervention as warranted. If delay is $>$ 28 days, discontinue TGR-1202.
 
If recurrence after rechallenge, resume at next lower dose level at discretion of the investigator.

Pulmonary & Related Infections*	
Grade 1 & 2	
Withhold TGR-1202 as warranted, provide supportive care and hold until complete resolution. Resume TGR-1202 at one dose lower.
 
If recurrence after re-challenge, discontinue TGR-1202.

Grade \geq 3	Discontinue TGR-1202 and intervene as warranted.

*While pneumonitis has been minimal with TGR-1202, it is a reported adverse event associated with other PI3K delta inhibitors. Use of anti-pneumocystis and anti-herpetic viral prophylaxis is required.
	
All Other Non-Hematological Adverse Events	
Grade \leq 2	Maintain current dose level.
Grade \geq 3	
Withhold TGR-1202 until Grade \leq 2.
 
If recurrence after re-challenge, resume at full dose or next lower dose level at discretion of the investigator.

Diarrhea and/or Colitis	
Diarrhea Grade \leq 2	
Maintain current dose level if tolerable or hold and then resume at current dose level once has resolved.
 
NOTE: If persistent grade 2 diarrhea, despite supportive care, delay TGR-1202 until \leq grade 1. If recurrence after re-challenge, resume at full dose or next lower dose level at discretion of the investigator.

Diarrhea Grade \geq 3	
Withhold TGR-1202 until Grade \leq 2. Resume at full dose or next lower dose level as per discretion of investigator.
 
If recurrence after rechallenge, resume at next lower dose level at discretion of the investigator.

Colitis (all Grades)	Hold TGR-1202. Treat with supportive care and after resolution of colitis, resume TGR-1202 at next lower dose level.

STUDY DRUG DOSE REDUCTION RECOMMENDATIONS

Study Drug	Starting Dose	1 st Dose Reduction	2 nd Dose Reduction
TGR-1202	800 mg	600 mg	400 mg

A maximum of two dose level reductions are allowed for TGR-1202.

If a patient requires a dose reduction of TGR-1202 due to study drug related toxicity, the dose may not be re-escalated. If further evaluation of the toxicity reveals the event was not related to TGR-1202, this must be recorded in the medical record and dose re-escalation to the next higher dose level may be considered at the discretion of the investigator.

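### Table 1 gives two different dosing instructions for a drug-related lung infection in a neutropenic patient and does not say which row governs

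*Combined protocol and SAP*

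**What the plan says.** Section 6.3.1, Table 1 sets out dose holds and reductions by type of event. Two of its rows matter here.

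- **Neutropenia row.** Its trigger is "Grade 4 neutropenia or occurrence of neutropenic fever or infection". Dosing is delayed until Grade 3 or lower "and/or neutropenic fever or infection is resolved", and the same sentence goes on to the restart at full dose: "neutropenic fever or infection is resolved; thereafter, resume at full dose". For a second event it says "If recurrence after rechallenge, resume at next lower dose level at discretion of the investigator".
- **Pulmonary & Related Infections row.** At Grade 1-2 the investigator is to "hold until complete resolution. Resume TGR-1202 at one dose lower". For a second event it says "If recurrence after re-challenge, discontinue TGR-1202". At Grade 3 or above it says "Discontinue TGR-1202 and intervene as warranted".

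A footnote to the pulmonary row gives background on pneumonitis ("While pneumonitis has been minimal with TGR-1202, it is a reported adverse event associated with other PI3K delta inhibitors") and requires prophylaxis. It says nothing about patients who are also neutropenic.

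Section 6.3 limits the guidance to events judged at least possibly due to study drug and exempts cytopenias caused by the lymphoma. The dose levels in Section 6.3.1 are 800, 600 and 400 mg. A reduction for drug-related toxicity may not be reversed.

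**The concern.** The neutropenia row treats infection as a trigger in its own right and does not limit it by site or grade. The pulmonary row makes no exception for neutropenic patients. A drug-related pneumonia during neutropenia therefore meets both rows as written, and their dose instructions cannot both be followed.

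What is at stake is patient safety and consistent dosing between sites. An investigator who follows the neutropenia row can point to the text when restarting 800 mg after a severe lung infection, although another row of the same table says to stop. An investigator who follows the pulmonary row makes a reduction that cannot be undone, or ends treatment.

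**Working it through.** **Step 1: the two rows side by side.** Take a patient on the starting dose of 800 mg.

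| Decision | Neutropenia row | Pulmonary row |
|---|---|---|
| End of hold | Neutropenia Grade 3 or lower and/or infection resolved | Complete resolution |
| First episode, Grade 1-2 | 800 mg | 600 mg (200/800 = 25% lower) |
| First episode, Grade 3 or above | 800 mg | Stop |
| Recurrence after a Grade 1-2 episode | Next lower level (600 mg), at discretion | Stop |

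The rows differ at all three dose decisions. They also differ on when the hold ends: the neutropenia row's and/or leaves open whether both conditions are needed, while the pulmonary row is clear.

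**Step 2: is there a tie-break?**

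- Sections 6.3 and 6.3.1 give a relatedness rule, a 28-day limit on delay, general recovery targets (hematologic Grade 3 or lower; non-hematologic Grade 2 or lower, or baseline), and the exemption for disease-related cytopenias. None ranks one row above another.
- Sections 4.4 and 6.2.2 allow treatment to stop for intolerable toxicity, and Section 4.4 also at investigator discretion. Neither says which row applies.
- The row for all other non-hematologic events gives way to the pulmonary row by its title. No such wording separates the neutropenia row from the pulmonary row.

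**Step 3: how often could it arise?** The plan gives no joint rate, so this is a rough range that assumes independence.

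Inputs:

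- Maximum enrollment (synopsis): 20 MZL + 20 WM = 40.
- Drug-related neutropenia, any grade (Section 7.1.1.2): 10% to 20%.
- Drug-related pneumonia, any grade (Section 7.1.1.3): 1% to below 10%.
- Grade 3 or higher neutropenia (synopsis and Section 1.4): 18%, from a pooled Phase I analysis. The synopsis states that the rates are all-causality and that combination therapy is included.
- Grade 3 or higher pneumonia with idelalisib (Section 1.1): 7%.

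Formula: expected patients = 40 × P(neutropenia) × P(pneumonia).

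- Any grade, low: 40 × 0.10 × 0.01 = 0.04.
- Any grade, high: 40 × 0.20 × 0.10 = 0.8; the true product is below this because the pneumonia band is below 10%.
- Grade 3 or higher neutropenia with any-grade pneumonia: below 40 × 0.18 × 0.10 = 0.72.
- Illustration with the other drug's severe pneumonia rate: 40 × 0.18 × 0.07 = 0.504.

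Three cautions apply. Neutropenia and infection are clinically linked, so independence may understate the overlap. Even if every drug-related pneumonia fell in a neutropenic patient, the expected count would be below 40 × 0.10 = 4; that is an arithmetic ceiling, not an estimate. Pneumonia also stands in for the whole pulmonary row, and the plan does not define which infections count as related. On the other side, the products count patients who have both events at any time, whereas the conflict needs them together.

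**The case against.** The strongest reply is that the rows are not alternatives. Table 1 is organised by adverse event, a patient with two events is managed under both entries, and an unconditional instruction to stop at Grade 3 or above leaves nothing to restart. On that reading the pulmonary row controls without being told to. The section is headed as recommendations and the table as guidance, the investigator may always stop, and PCP and antiviral prophylaxis is mandatory. By the figures above, fewer than one patient is likely to be affected.

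Most of this stands. It is the more natural reading and probably the intended one, and it makes the point minor. It does not remove the conflict. The neutropenia row addresses the infection itself, not just the neutrophil count, so it too can claim to be the specific rule. Discretion to stop does not tell an investigator which row to follow.

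Two stronger readings are tempting but unsupported. A reader might infer that the protocol directs full-dose re-exposure after severe lung infection. It does not: it permits that under one row while another says to stop, within guidance that leaves room for judgment. A reader might also infer that pneumonitis has no row and would be handled with the other non-hematologic events. The footnote attached to the pulmonary row already signals that it belongs there.

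**Conclusion.** The conflict is real and can be checked within one table. For a drug-related pulmonary infection in a neutropenic patient, Table 1 gives 800 mg or 600 mg after a first Grade 1-2 episode, 800 mg or discontinuation after a first Grade 3 or higher episode, and a discretionary reduction or discontinuation on recurrence. No text ranks the two rows.

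Its weight is small. The expected overlap is under one of 40 patients, assuming independence and taking pneumonia to represent the pulmonary row; the documents cannot confirm either assumption. The case for acting rests on the consequence for the rare patient affected and on how little the correction takes. Nothing here implies a problem with the response or progression analyses. This is a cheap improvement to a safety instruction.

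**What to change.** Add one sentence to the neutropenia row of Table 1: *For any pulmonary or related infection, the Pulmonary & Related Infections row governs dose and discontinuation regardless of neutrophil count; where re-treatment is allowed, also wait until neutropenia is Grade 3 or lower.*

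This makes the probable intent explicit, keeps the neutropenia row's own recovery condition, and removes the and/or doubt for lung infections. Leave the heading of the pulmonary row as it is; a new title is not needed and could narrow its scope.

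The change needs no new visits, data or analyses. The downside is that a patient who might have been re-challenged at full dose would instead be reduced or stopped.

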6.4 ORDERING TGR-1202

Once the clinical study site receives regulatory approval (IRB/IEB), and the Sponsor and/or Sponsor designee performs the Site Initiation Visit and inspection of pharmacy, and determines the site to be officially open for enrollment, and once a patient is identified, a shipment of pre-determined quantity of TGR-1202 will be shipped to the clinical study site.

Upon receipt of treatment supplies, the Pharmacist or the appropriate person of the site should update the accountability forms for TGR-1202. If any abnormality on the supplied bottles (TGR-1202) is observed, the Pharmacist or the appropriate person must document that on the acknowledgement of receipt and contact that Sponsor and/or Sponsor designee.

6.5 DURATION OF THERAPY

In the absence of treatment delays due to adverse event(s), treatment should continue through Cycle 1 and beyond unless one of the following criteria applies:

- Disease progression or inter-current illness that prevents further treatment,
- Patient decides to withdraw from the study, or changes in the patient's condition render the patient unacceptable for further treatment in the judgment of the investigator.

During the study period, all patients will be evaluated for response by CT, PET-CT and/or MRI every 3 cycles. For patients with WM without nodal involvement, response will be assessed by quantitative monoclonal IgM protein every 3 cycles. The best clinical response as well as disease progression will be determined by local investigator. Patients will remain on study treatment until the occurrence of definitive disease progression, unacceptable toxicity, or withdrawal from the study due to investigator decision or other reasons. Patients who discontinue from study treatment (either for toxicity or physician choice) and have not progressed will continue to be followed for progression approximately every 6 months or per standard of care.

7 STUDY MEDICATIONS OVERVIEW AND SAFETY

7.1 TGR-1202(UMBRALISIB)

Chemical Name:	Umbralisib
Other Name:	TGR-1202
Classification:	Phosphatidylinositol-3-Kinase (PI3K) Delta Inhibitor
Formulation:	See Investigator Brochure
Mode of Action:	Irreversibly inhibits activity of the Class I Delta isoform of PI3K
How Supplied:	TGR-1202: 200 mg tablets
Storage:	Store at 25°C. Excursions permitted 15°C to 30°C.
Stability:	Retest dates will be provided periodically by Sponsor.
Route of Administration:	Oral
Packaging:	TGR-1202 is provided in HDPE bottles each containing 30 tablets and a silica gel canister as a desiccant.
Availability:	TGR-1202 is available from TG Therapeutics.

7.1.1 COMPREHENSIVE ADVERSE EVENTS AND POTENTIAL RISKS LISTS (CAEPRS)

The following adverse events were observed in patients treated with single agent TGR-1202 and were considered at least possibly related to study medication. See the TGR-1202 investigator brochure for a complete list of all adverse events reported regardless of causality.

7.1.1.1 COMMON (>20%)

- **Gastrointestinal Disorders:** Diarrhea, Nausea
- **General Disorders and Administration Site Conditions:** Fatigue

7.1.1.2 LESS COMMON (≥10% - ≤ 20%)

- **Blood and Lymphatic System Disorders:** Neutropenia
- **Gastrointestinal Disorders:** Vomiting
- **Metabolism and Nutrition Disorders:** Decreased Appetite
- **Skin and Subcutaneous Tissue Disorders:** Rash

7.1.1.3 UNCOMMON (≥1 - <10%)

- **Blood and Lymphatic System Disorders:** Anemia, Febrile neutropenia, Leukocytosis, Thrombocytopenia
- **Eye Disorders:** Vision Blurred

- **Gastrointestinal Disorders:** Abdominal distension, Abdominal pain, Constipation, Dry mouth, Dyspepsia, Colitis
- **General Disorders and Administration Site Conditions:** Asthenia, Chills, Oedema peripheral, Pyrexia
- **Infections and infestations** Oral candidiasis, Pneumonia, Upper respiratory tract infection
- **Investigations:** Alanine aminotransferase increased, Aspartate aminotransferase increased, Blood creatinine increased, Lymphocyte count increased, Weight decreased
- **Metabolism and Nutrition Disorders:** Dehydration, Hyperglycemia, Hypokalemia, Hypophosphatemia,
- **Musculoskeletal and Connection Tissue Disorders:** Arthralgia, Muscle spasms, Pain in extremity
- **Nervous System Disorders:** Dizziness, Dysgeusia, Headache, Neuropathy peripheral, Tremor
- **Psychiatric Disorders:** Insomnia
- **Respiratory, Thoracic and Mediastinal Disorders:** Cough
- **Skin and Subcutaneous Tissue Disorders:** Alopecia, Night sweats, Pruritus

7.1.1.4 EVENTS REPORTED IN LESS THAN 1% OF SUBJECTS

- **Blood and Lymphatic System Disorders:** Leukopenia, Hyperbilirubinemia, Bacteremia
- **Ear and Labyrinth Disorders:** Tinnitus
- **Eye Disorders:** Visual Impairment, Visual acuity reduced
- **Gastrointestinal Disorders:** Eruption, Flatulence, Gastroesophageal Reflux Disease, Abdominal Pain Upper, Mouth Ulceration, Anal Hemorrhage, Hypoaesthesia Oral, Paraesthesia Oral, Pancreatitis
- **General Disorders and Administration Site Conditions:** Malaise, Mucosal Inflammation,
- **Hepatobiliary Disorders:** Hypocalcemia
- **Infections and Infestations:** Candida infection, Fungal skin infection, Lung infection, Sinusitis
- **Investigations:** International Normalized Ratio Increase, Blood lactate dehydrogenase increase, Blood phosphorus increased, Blood sodium increased, Blood uric acid increased, White blood cell count decreased
- **Injury, Poisoning and Procedural Complications:** Contusion
- **Metabolism and Nutrition Disorders:** Hyperlipidemia, Hypertriglyceridemia, Hyponatremia
- **Musculoskeletal and Connective Tissue Disorders:** Muscular Weakness, Myalgia, Pain in Jaw
- **Nervous System Disorders:** Somnolence, Peripheral Sensory Neuropathy, Memory Impairment
- **Psychiatric Disorders:** Anxiety, Libido Decrease, Delirium, Parasomnia
- **Reproductive System and Breast Disorders:** Erectile Dysfunction
- **Respiratory, Thoracic and Mediastinal Disorders:** Dyspnea, Epistaxis, Hypoxia, Influenza, Respiratory Failure
- **Skin and Subcutaneous Tissue Disorders:** Dermatitis, Dermatitis Acneiform,
- **Vascular Disorders:** Hot Flush

8 MEASUREMENT OF EFFECT

During the study period, all patients will be evaluated for response by CT, PET-CT and/or MRI every 3 cycles. All baseline assessments to characterize disease will be performed within 30 days of Cycle 1 Day 1, prior to initiation of therapy. During the treatment period, all efficacy assessments have a +/- 7 day window. The determination of response and progression will be based on the Response Criteria for non-Hodgkin's lymphoma, Lugano Classification (Cheson et al., 2014) and IWWM-6 (Owen et al 2013) consensus for respective disease histology. The best clinical response as well as disease progression will be determined by the independent central radiology group (ICRG). The findings of the ICRG will be considered primary for analyses of ORR, PFS, and other tumor control endpoints. Patients who discontinue from study treatment (either for toxicity or physician choice) and have not progressed will continue to be followed for progression approximately every 6 months or per standard of care.

8.1 METHOD OF ASSESSMENT

CT scan is the preferred method for radiographic tumor assessment. CT with iodinated IV contrast is preferred. If iodinated contrast is contraindicated, a non-contrast chest CT coupled with a gadolinium-enhanced MRI of the abdomen/pelvis is an acceptable substitute. Contrast-enhanced scanning is preferred, but iodine-containing or gadolinium contrast material may be omitted in patients for whom use of a contrast agent would be medically contraindicated. Chest x-ray, ultrasound, endoscopy, laparoscopy, or tumor markers will not be considered for response assessment. PET-CT may also be used if per standard of care by investigator.

Bone marrow assessment should be used to assess response to therapy if the patient was deemed to have disease in the bone marrow prior to initiation of protocol therapy, per standard of care and at the discretion of the investigator.

For radiographic evaluations, the same method of assessment and the same technique (e.g., scan type, patient position, dose of contrast, injection/scan interval) should be used to characterize each identified and reported lesion at baseline and during study treatment and follow-up. However, if a patient is imaged without contrast at baseline, subsequent assessments should be performed with contrast, unless medically contraindicated.

8.2 RESPONSE REVIEW

All responses will be made by local investigator assessment.

8.3 ANTITUMOR EFFECT

Assessment of lymphoma response (CR, PR, VGPR or MR) and disease progression will be evaluated as outlined in the schedule of events, according to the Response Criteria for non-Hodgkin's lymphoma, Lugano Classification (Cheson et al., 2014) and IWWM-6 consensus (Owen et al 2013) for respective disease histology. Overall response rate, CR, PR, VGPR, MR, SD, PFS and DOR will be calculated as detailed below.

8.4 DEFINITIONS OF TUMOR RESPONSE AND PROGRESSION

Evaluable for objective response. Only those patients who have had a pre-treatment baseline efficacy evaluation and at least one post-treatment efficacy evaluation will be considered evaluable for response. These patients will have their response classified according to the definitions stated below.

8.4.1 COMPLETE RESPONSE

Complete response (CR) is defined as the complete disappearance of all evidence of disease and disease-related symptoms. The spleen and/or liver, if considered enlarged before therapy, on the basis of physical exam or CT scan, should not be palpable on physical examination and should be considered normal size by imaging studies, and nodules related to lymphoma should disappear. Bone marrow infiltrate cleared on repeat biopsy, if indeterminate by morphology, immunohistochemistry should be negative (Cheson et al., 2014 Lugano Classification).

Previously involved nodes that were 1.1 to 1.5 cm in the long axis and more than 1.0 cm on their short axis before treatment must have decreased to ≤ 1.0 cm in their short axis after treatment (Cheson et al., 2014 Lugano Classification).

For Waldenstrom's macroglobulinemia patients, complete response is defined as disappearance of serum monoclonal IgM protein by immunofixation with a normal serum IgM level. The spleen and/or liver, if considered enlarged before therapy, on the basis of physical exam or CT scan, should not be palpable on physical examination and should be considered normal size by imaging studies, and nodules related to WM should disappear. Bone marrow infiltrate cleared on repeat biopsy, if indeterminate by morphology, immunohistochemistry should be negative. (Owen et al 2013)

